14.1 Case report forms and data collection

Case report forms

The clinical investigation data will be collected via pCRF completed by the site's responsible persons and finally approved by the principal investigator. The CRF pages will consist of one original and two copies of each page using "No Carbon Required" (NCR) paper.

The site will archive one copy of the completed CRF with the investigator file. Completed CRF originals (i.e. the top page of the NCR paper) will be transferred to the data management of the sponsor's designee and one copy will be sent to the sponsor's designee project management

Data entering into the pCRF

All data must be entered in English. The pCRFs should always reflect the latest observations on the subject's participation in the trial. Therefore, the pCRFs should be completed as soon as possible during or after the subject's visit. It is the investigators' obligation to assure documentation of all relevant data in the patient's file, such as medical history, concomitant diseases, date of clinical trial enrolment, visit dates, results of examinations, administrations of medication, and AEs. The investigator must verify that all data entries in the pCRFs are accurate and correct. If some assessments are not done, or if certain information is not available, not applicable or unknown, the investigator should indicate this in the pCRFs. The investigator will be required to sign and date the clinical data.

The query process

The monitor will review the pCRFs and evaluate them for completeness and consistency. Each pCRFs will be compared with the respective source documents to ensure that there are no discrepancies between critical data. All entries, corrections, and alterations are to be made by the investigator or authorized designee. Any CRF corrections should be made in a way that does not obliterate the original entry. Investigators or designees must sign with their initials and date all corrections.

Any change or addition after separation of the NCR sets must be made using Data Clarification Forms (DCFs).

The investigator or designee has to carefully answer all queries issued on DCFs. Corrections necessary after the CRF has been collected from the site must be documented in a DCF. A copy of the DCF must be retained with the respective CRF at the site.

14.2 Subject records and source data

The data reported in the pCRF shall be derived from source documents and consistent with these. Certain data may be recorded directly in the pCRF, which will then be considered as source data. Source documents are all documents used by the investigator or hospital that relate to the subject's medical history, that verify the existence of the subject, the inclusion and exclusion criteria, and all records covering the subject's participation in the clinical investigation. They include laboratory notes, memoranda, material dispensing records, subject files, etc. The origin of source data in the clinical investigation will be further specified in a separate document ("Origin of Source Data").

It is the responsibility of the investigator and all responsible personnel at site to maintain source documents and to record essential information in the medical records in accordance with national regulations and requirements:

- Study code;
- Subject screening number and subject number;
- Confirmation and date that informed consent for participating in the study was obtained;
- Diagnosis;
- All visits during the clinical investigation period;
- All AEs/ADEs;
- Treatments and medications.

The investigator is responsible for ensuring the accuracy, completeness, legibility and timeliness of the data recorded in the pCRF. The investigator must submit a completed pCRF for each subject who signed the consent form. Any supportive documentation submitted with the pCRF, such as laboratory or hospital records, should be clearly identified with the clinical investigation ID and subject number. Any personal information, including subject name, should be removed or rendered illegible to preserve individual confidentiality.

14.3 Data management procedures

Details on data handling will be described in the Data Management Plan (DMP). The sponsor's designee will handle the data cleaning process, including logical check, medical checks, and query processes. Computerized validation check programs on completeness, correctness,

plausibility (such as range checks, cross-checks) will verify the data according to the Data Validation Plan (DVP). All identified discrepancies will be queried using DCFs and will be addressed to the investigator. The database will be soft locked when it is considered complete and accurate (i.e. all CRF pages entered, all data cleaning activities performed). The database will be hard locked after all the changes following the DRM have been done and the database is considered complete and accurate. All changes will be tracked (audit trail). Sponsor approval prior to database hard lock is mandatory.

14.4 Data retention

The investigator shall retain all study records during the clinical investigation and for the period required by the applicable regulatory requirements or for at least 15 years after the premature termination or completion of the clinical investigation, whichever is the longer. However, the investigator should contact the sponsor prior to destruction of any records or reports pertaining to the clinical investigation in order to ensure they no longer need to be retained.

The investigator must take measures to prevent accidental or premature destruction of these documents. Included in records to be retained are the subjects' medical records, signed CIP, signed consent forms, EC approval letters, product accountability records, correspondence concerning the clinical investigation and any other documents to identify the subjects (including the Subject Identification Log).

The medical files of study subjects must be retained in accordance with local legislation and in accordance with the maximum period of time permitted by the hospital, institution or private practice.

14.5 Report of the clinical investigation

A final report of the clinical investigation (a "Clinical Investigation Report") will be completed, even if the clinical investigation is prematurely terminated. The report will be prepared by FGK according to ISO 14155:2011.

The report will be submitted to regulatory authorities and ECs, as appropriate, within the timeframes defined per national regulation or by the EC.

15 Ethical and regulatory considerations

15.1 Good Clinical Practice

The investigator will ensure that this study is conducted in full conformity with the currently acknowledged revision of the Declaration of Helsinki. By acting in accordance with this CIP the study site fulfills the requirements of the International Standard ISO 14155:2011 (Clinical investigation of medical devices for human subjects - Good clinical practice [GCP]).

15.2 Ethics Committee

Before the initiation of the clinical investigation, the final CIP, any amendments if applicable, the subject information sheet and consent form, as well as any additional documents which are required by national regulations and the EC will be submitted to the competent EC for review. A favorable opinion for the clinical investigation must be obtained from the EC before any subject is enrolled at a center.

If appropriate, any additional requirements imposed by the EC will be followed. Amendments to the study documents will be notified to, or approved by, the EC before implementation, if applicable.

15.3 Regulatory requirements

This clinical investigation will be submitted for authorization to the CA as required by national law. The clinical investigation will not be initiated until written authorization for the conduct of the clinical investigation, has been received from the CA. Amendments to the clinical investigation will also be submitted for authorization to the CA as applicable.

15.4 Insurance

Insurance coverage for damages emerging from the clinical investigation will be provided according to applicable legal requirements. In addition, the sponsor has taken out insurance coverage for the subjects' travelling from their homes/places of work to the site and back. During the informed consent procedure, the investigator must inform the subject accordingly. Insurance details will be provided to the subject within the subject information sheet.

15.5 Informed consent process

Before any clinical study-related activities are performed, the investigator (or authorized designee) must review the ICF and explain the clinical investigation to potential study subjects. The investigator must ensure that the subject is fully informed about the aims, procedures, potential risks, any discomforts, and expected benefits of the clinical investigation. Before consenting, the subject must be left with ample time to consider and ask questions. It must be emphasized that participation is voluntary and that the subject has the right to withdraw from the clinical investigation at any time without prejudice. The subjects must then sign and date the ICF prior to the conduct of any study procedures. The investigator must sign and date the ICF as well.

Subjects will be informed that there is a chance they may not receive the treatment due to either not meeting the eligibility criteria or the target number of subjects to be randomized into the clinical investigation having been met.

A copy of the subject information and ICF will be given to the subjects for their records. The rights and welfare of the study subjects will be protected by emphasizing to them that the quality

of their medical care will not be adversely affected if they decline to participate in this clinical investigation.

If amendments to the final CIP affect the subject's participation in the clinical investigation (e.g. a change in any procedure), the subject information and ICF must be updated to incorporate this modification, and subjects must agree to sign the amended form indicating that they re-consent to participate in the clinical investigation.

15.6 Subject confidentiality

The study CIP, documentation, data, and all other information generated will be held in strict confidence. No information concerning the clinical investigation or the data will be released to any unauthorized third party without prior written approval of the sponsor.

Personal subject data will be kept confidential in compliance with the European Data Protection Directive [8] or the EU General Data Protection Regulation 2016/679 [9], as applicable, and other applicable international and national requirements.

The investigator must ensure that the pseudonymization (coding) of study subjects will be maintained and that their identities are protected from unauthorized parties. On pCRFs, compensation documentation, or any other documents submitted to the sponsor or sponsor's representative, subjects must be identified only by their identification codes; it is not allowed to use their names, addresses, telephone numbers, or similar information. The investigator will keep the original of the Subject Identification Log (including complete name and date of birth of each subject) in his/her file. The investigator must maintain these documents in strict confidence.

To allow compliance with GCP, all subjects will be asked for consent regarding the access to their personal clinical study-related data for monitoring, audits, and inspections as well as regarding transmission and storage of their pseudonymous data; a respective statement will be part of the ICF. Professionals getting access to source data for monitoring, audits and inspections are bound to preserve strict confidentiality.

16 Amendments to and deviations from the CIP

16.1 Amendments

Any change to the CIP concerning the purpose of the study, the study design or the subject's eligibility can only be made in form of a written amendment to the CIP. Such amendments have to be discussed and signed by the sponsor, the coordinating investigator, and the principal investigator(s) before implementation (see also Section 15.2).

Amendments that might have an impact on study procedures to be performed and/or the well-being of the subject require a further ICF that is to be signed by all subjects enrolled in the clinical investigation who are affected by the amendment.

The sponsor or sponsor's representative will distribute CIP amendments to the investigators.

16.2 Deviations

A CIP deviation is a failure to follow, intentionally or unintentionally, the requirements of the CIP. As required by national regulation or guidelines, requests for deviations and reports of deviations will be provided to the EC if the deviation affects subject's rights, safety and well-being, or the scientific integrity of the clinical investigation.

Under emergency circumstances deviations from the CIP may proceed without prior approval by the sponsor and favorable opinion of the EC if the rights, safety and well-being of human subjects need to be protected. Such deviations will be documented and reported to the sponsor and the EC as soon as possible in accordance with national regulations.

Where the monitor or sponsor identifies that the investigator is out of compliance, this will be notified to the investigator in writing, with a request to correct the source of the deviation immediately. Corrective action will be implemented to avoid repeated non-compliance, which will usually include re-training and may include terminating the clinical investigation at the site. Depending on the nature of such deviations, they will either be recorded by the investigator on the paper deviation form or completed by the monitor via the paper deviation form and signed by the investigator.

All CIP deviations will be listed and if the subjects concerned will be evaluable for analysis will be discussed in a data review meeting prior to the statistical analysis.

The sponsor is responsible for analyzing deviations and assessing their significance. Corrective action will be implemented to avoid repeated deviations, which may include suspending the clinical investigation and/or amending the CIP.

17 Suspension or premature termination of the clinical investigation

The sponsor reserves the right to terminate or suspend the clinical investigation for any reason (e.g. safety reasons, new data on the risk/benefit assessment, ethical or administrative reasons). Written notice, outlining the reasons for the termination, will be submitted to the investigators in advance of such termination. The sponsor will provide instructions if assessments beyond the regular per protocol procedures should be necessary.

The sponsor may suspend enrollment or terminate the study at a specific site for reasons including, but not limited to, inadequate data collection, low subject enrollment rate, achievement of the total subject number, or non-compliance with the CIP or other clinical research requirements.

A principal investigator, EC, or regulatory authority (if applicable) may also suspend or prematurely terminate the clinical investigation at the investigational sites for which they are responsible.

In terminating the clinical investigation, the sponsor and the investigator(s) will assure that adequate consideration is given to the protection of subjects' interests.

If the clinical investigation is prematurely terminated, the sponsor or its representative will promptly inform the CA of the termination and its reason(s); the investigator or the sponsor (or representative) will promptly inform the EC, as specified in applicable regulations.

Permission to resume the clinical investigation after a temporary halt will be obtained from the CA and EC prior to implementation. The investigators will not resume the clinical investigation until the sponsor instructs them to do so and has confirmed that the necessary approvals are in place.

In case a patient was treated with the investigational device when the clinical investigation is suspended or prematurely terminated, every effort should be made to arrange for a final examination of such patient. Further medical care will be according to standard care at that site.

18 Unblinding

The premature breaking of the blinding code should be restricted to emergency cases in which knowledge of the administered treatment is necessary, e.g. after occurrence of SADEs or in case of detected pregnancy which has existed during treatment with the medical device but had not been detected prior treatment. Whenever possible, the medical monitor or sponsor should be contacted before breaking the blinded emergency code. Should any code be broken, the respective patient will be withdrawn from further participation in the study and a written explanation must be given by the investigator; the sponsor must be notified immediately.

19 Publication policy

In the following abbreviations are listed as used within this statistical analysis plan or which might occur within the tables, listings and graphs outputs:

AE	Adverse event
ANCOVA	Analysis of covariance
ATC	Anatomical therapeutic chemical classification
BDRM	Blind data review meeting
BMI	Body mass index
CI	Confidence interval
CRF	Case report form
FAS	Full analysis set
ICH	International council of harmonization
HIT	Headache impact test
H_0	Null hypothesis
H_1	Alternative hypothesis
MedDRA	Medical dictionary for regulatory activities
MSQ	Migraine-specific quality of life questionnaire
N	Number of subjects
PGI-S	Patient global impression of severity
PP	Per-protocol
Q1	1 st quartile
Q3	3 rd quartile
SAE	Serious adverse event
SAF	Safety analysis set
SAP	Statistical analysis plan
SD	Standard deviation
SOC	System organ class
TLG	Tables, listings, graphs
V	Visit

1 General

This Statistical Analysis Plan (SAP) was defined by the Sponsor and the responsible Statistician without knowledge of the randomization code. It is based upon the Study Protocol (version 7.0 of 14Jun2021) and contains detailed description of the statistical methods described therein.

The SAP describes prospectively the analyses to be performed on study data. It was finalized prior to data base lock and unblinding.

This is a randomized, placebo-controlled, double-blind, multicenter clinical investigation of a medical device. The study consists of a 4-week screening period, a 6-week treatment period (2 weeks run-in and a 4-week observation window to assess the treatment effect), and a 4-week follow-up period.

Subjects who provided written informed consent and are eligible for the study will be asked to complete a daily diary for 4 weeks during the screening period. In the diary the subjects will record headache and migraine days, any changes in their health, and concomitant medications they may be using. The data collected in the diary during this screening period will be used as Baseline for the performance assessments.

Subjects who completed the screening period and continue to meet the eligibility criteria after review of diary entries by the investigator will be randomized (stratified by medication overuse) in a 1:1 ratio to receive either active or placebo treatment. The subjects will receive 6 treatments with the Chordate System S211 at weekly intervals at the site (Day 0 to 35; treatment Visit [V] 1 to 6) and continue to maintain a daily diary. One week after the last treatment, an end of treatment visit will be performed on Day 42 (V7).

After completion of the 6-week study treatment period (V1 to V7), subjects will be followed up for another 4 weeks. The final visit will be performed on Day 70, 5 weeks after the last study treatment. During the 4-week follow-up, the subjects will continue to complete a daily diary.

The study will be performed according to a 2-stage group-sequential design with one interim analysis that allows the premature termination of the study due to efficacy or futility or adaption of the sample size.

Approximately 148 subjects will be enrolled to achieve at least 132 subjects evaluable for the primary performance endpoint (assuming a drop-out rate of 10%), with 66 subjects receiving treatment with the Chordate System S211 and 66 subjects receiving treatment with the Chordate System S211 in placebo mode. If, during the conduct of the study, the drop-out rate proves to be higher than expected (>10%), enrollment will continue until at least 132 subjects were assessed for the primary endpoint. A group-sequential design with one interim analysis after approximately 50 subjects have completed the 6-week study treatment period will be used. It will allow the premature termination of the study due to efficacy or futility or adaption of the sample size.

At the time of finalization of this SAP, the interim analysis had been carried out and did not lead to any adaption of the study.

An additional unblinded subgroup analysis (the unblinded analysis of the German subjects) will be performed and will include selected analyses only. Details on which outputs will be produced for additional unblinded subgroup analysis are given in Appendix A.

2 Performance and Safety Endpoints

2.1 Primary Performance Endpoint

The primary performance endpoint is given by the mean change from Baseline (4-week screening period) in 4-week headache days with moderate to severe intensity in 4-week performance assessment period (V3 to V7).

2.2 Secondary Performance Endpoints

The following secondary performance endpoints will be analyzed:

- Mean change from Baseline in 4-week headache days with moderate to severe intensity in follow-up period;
- Mean change from Baseline in 4-week migraine days;
- Mean change from Baseline in 4-week headache days (mild, moderate and severe intensity) in 4-week performance assessment period (V3 to V7);
- Proportion of subjects with 30% or greater reduction in headache days of moderate to severe intensity;
- Proportion of subjects with 50% or greater reduction of headache days of moderate to severe intensity;
- Change in the use of acute (abortive) medication;
- Change in migraine-specific quality of life questionnaire (MSQ), headache impact test-6 (HIT-6), and patient global impression of severity (PGI-S).

2.3 Safety Endpoint

- Frequency, severity, device-relationship, and outcome of AEs

3 Statistical Analysis Sets

3.1 Safety Analysis Set

The safety analysis set (SAF) will include all subjects who were treated with the investigational medical device at least once, irrespective of the duration of use. Subjects will be analyzed as treated.

3.2 Full Analysis Set

The full analysis set (FAS) will include all subjects included in the SAF and having baseline and any post baseline data of any performance endpoint (primary performance endpoint or any of the secondary endpoints). Subjects will be analyzed as randomized.

3.3 Per-Protocol Set

The per-protocol analysis set (PP) will include all subjects who fulfill the following criteria:

- Included in the FAS.
- Do not have any other major protocol violations which will affect the assessment of efficacy. An example of a major protocol violation is a subject who terminates the study participation before the primary endpoint follow-up or violation of the inclusion/exclusion criteria.
- Have no imputation for the primary performance endpoint (i.e. completed the diary for 28 days after V3).
- Have full duration of study treatment.

Subjects will be analyzed as treated.

3.4 Assignment of Analysis Sets to Analysis

Primary efficacy analysis will be based on the FAS. A sensitivity analysis of the primary endpoint will be performed using the PP set. All secondary efficacy outcomes will exploratorily be analyzed using the FAS and PP set. Safety analyses will be based on the SAF.

4 Statistical Evaluation

The investigator will review the patient's diary and enter the number of days with headache and the number of days with migraine in the eCRF. This information will be available for the baseline period, the performance assessment period and the follow-up period.

In case a patient should have documented less than 28 days per period (but has a compliance of at least 80%), the number of headache days per period is derived as follows:

Number of headache days = (Number of headache days x 28) / Number of days observed

If a patient has a diary compliance of less than 80%, this period will not be used for statistical analysis of this endpoint.

For example, if a patient documented 24 days for one period only, and documented 6 days with headache, the derived number of headache days in this period is calculated to $(6 \times 28) / 24 = 7$.

The assessments done before start of treatment will serve as baseline evaluations. Generally, a baseline measurement refers to the last non-missing assessment made before treatment start.

Continuous data are presented with the number of observations, mean value, standard deviation (SD), minimum, 1st quartile (Q1), median, 3rd quartile (Q3), and maximum value. Categorical data are presented as counts and percentages. In general, minimum and maximum will be presented to the same level of precision as the raw data; means and medians, SD, and quartiles will be presented to one further decimal place. Categorical variables will be presented by frequency tables, using number and percentage. Percentages will be presented to one decimal place.

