11.5.2 Treatment

Visit 1 (Day 0)

Prior to any study related assessment the investigator will do a SARS-CoV-2 test, if required by site policy. If the test result is positive the patient will be asked to take the measures, which the authorities require in this case. The patient may come back to the site and continue the study after these requirements are fulfilled and a negative test result is present.

Afterwards the investigator will discuss with the subject any changes in their health during the screening phase and any changes in their medication or any new concomitant medication they may have used. The investigator will also review the subject's paper diary entries and ensure that the diary has been completed accurately. Additionally, the following assessments will be performed:

- Completion of questionnaires (HIT-6, MSQ);
- Assessment of PGI-S.

Subjects who continue to meet all inclusion criteria and none of the exclusion criteria will be randomized to 1 of the 2 study treatments.

Randomized subjects will be treated as described in Section 11.2.1 and detailed in the IFU. Any AEs or device defects occurring during or after treatment will be documented in the pCRF.

Visits 2, 3, 4, 5, and 6 (Day 7, 14, 21, 28, and 35 [± 3 days each])

At each visit, subjects will receive study treatment as described in Section 11.2.1 and detailed in the IFU.

At Visit 3 additionally the following assessments will be performed:

- Completion of questionnaires (HIT-6, MSQ);
- Assessment of PGI-S.

The subjects will be asked about any AEs and changes in concomitant medication since the last visit and any new or changed information will be documented in the pCRF.

Visit 7 (Day 42 ± 3 days)

The following assessments will be performed:

- Documentation of AEs;
- Documentation of changes in concomitant medication;
- Completion of questionnaires (HIT-6, MSQ);
- Assessment of PGI-S.

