The listings are always sorted by treatment group, center, and subject. If a different sorting order should be used for some listings this will be remarked separately. The variables for the special listings are explicitly given in the description of listings. All listings will be presented for the safety analysis set, if not stated differently, and indicator variables for further analysis sets, e.g., full analysis set, will be added.

Screened but not treated subjects (e.g. withdrawal before treatment) will be considered in tables and listings describing disposition of subjects, analysis sets and discontinuation as well as listings for subject demographics and migraine history.

The following title will be used for all generated tables, listings, and graphs:

PM007 – Final Analysis

Page # of #

<Subtitle for description of contents - if applicable>

<Analysis set>

The numbering NNN of the tables/listings/graphs will be stated in the detailed description (Appendix A).

Following footnote will be used for all generated tables, listings, and graphs:

Date: <Actual date(ddmmmyyyy)>

Program: <Name of program>

The statistical evaluation will be performed using SAS version 9.4 or higher.

5 Changes from Protocol

- The wording “monthly headache days” was changed to “4-week headache days” in order to avoid confusion. The analysis is based on 4 week (28 day) assessment windows and not on calendar months (30 days).
- For PGI-S no Wilcoxon test for change from baseline will be performed, since this is a categorical parameter.
- Secondary efficacy outcomes will also be analyzed for the PP set.
- An additional unblinded subgroup analysis (the unblinded analysis of the German subjects) will be performed.
- No Van Elteren test will be used for primary performance endpoint if the data is not normally distributed as no adjustment of alpha is possible according to group-sequential design with O’Brien & Fleming alpha spending function. The ANCOVA will be used even if the normal distribution cannot be shown. Due to the large sample size, it can be assumed that the data are approximately normal distributed.

6 Literature

Bayliss, M. S., & Batenhorst, A. S. (2002). *The HIT-6 TM A User's Guide*. Research Triangle Park, NC: QualityMetric Incorporated, Lincoln, RI and GlaxoSmithKline.

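### Does the absence of a stated first and last diary day leave the primary headache-day count open to long, unscaled periods?

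*SAP*

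**What the plan says.** SAP Section 2.1 defines the primary endpoint as the change in headache days of "moderate to severe intensity in 4-week performance assessment period (V3 to V7"). Protocol Section 11.5.2 sets the treatment visits as "Visits 2, 3, 4, 5, and 6 (Day 7, 14, 21, 28, and 35 [± 3 days each"]) and the end-of-treatment visit as "Visit 7 (Day 42 ± 3 days").

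SAP Section 4 has the investigator review the diary and "enter the number of days with headache and the number of days with migraine in the eCRF". The adjustment for incomplete diaries begins "In case a patient should have documented less than 28 days per period (but has a compliance of at least 80" percent) and multiplies the count by 28 over the days observed. Below the threshold, "If a patient has a diary compliance of less than 80%, this period will not be used for statistical analysis of this endpoint". Protocol Section 13.2 carries the same rules, and SAP Section 4.5 allows no other imputation of diary data.

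Two further statements bear on the window. SAP Section 3.3 requires of the per-protocol set: "Have no imputation for the primary performance endpoint (i.e. completed the diary for 28 days after V3"). SAP Section 5, explaining the move away from monthly wording, says "The analysis is based on 4 week (28 day) assessment windows and not on calendar months (30 days"). Protocol Section 11.5.1 also describes screening as a 28-day diary phase.

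**The concern.** Two descriptions of one period sit side by side: an interval between two visits, and a run of 28 days from V3. They coincide only when V7 falls exactly 28 days after V3. The visible text does not say which diary day is first or last, whether the V3 day counts, where the follow-up count starts, or what the 80% is a percentage of.

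If sites counted from visit to visit, short periods would be scaled up to 28 days while long ones kept their raw count. For one patient this could be large. At an assumed rate of 15 headache days per 28, a 34-day period yields 15 × 34/28 = 18.2, an excess of 3.2 days against a design difference of 3. With a 28-day baseline, a true 50% reduction would show as 1 − 0.5 × 34/28 = 39%. The worry is therefore noise in the primary change score, misclassified responders, and a derivation that could still be chosen late.

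**Working it through.** **1. The plan's own figure.** SAP Section 4 scales 6 headache days in 24 documented days: 6 × 28/24 = 7. This reproduces exactly.

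**2. Interval lengths if counted visit to visit** (visit windows from the protocol's schedule and Section 11.5)
- Performance period: shortest (42 − 3) − (14 + 3) = 22 days; longest (42 + 3) − (14 − 3) = 34 days.
- Follow-up: the same arithmetic on Days 42 and 70 gives 22 to 34 days.
- Baseline: 28 ± 3, so 25 to 31 days.
- Largest inflation: 34/28 = 1.214 for performance, 31/28 = 1.107 for baseline.

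**3. Which reading fits the SAP?** Take a patient with a perfect diary whose V7 falls 25 days after V3. The diary runs daily to the follow-up visit (Protocol Section 11.4.1), so this patient has completed 28 days after V3. By SAP Section 3.3 the endpoint is therefore not imputed. Counted visit to visit, SAP Section 4 would nevertheless scale the 25-day count by 28/25. The two sections then contradict each other. With independent offsets uniform on ±3 days (an assumption), 21/49 = 42.9% of performance periods are shorter than 28 days, so that share of perfect diarists would count as imputed. Under a fixed 28-day window from V3 the two sections agree: only a diary gap triggers scaling.

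**4. Are the days available?** The fixed window ends at V3 + 28: Day 11 + 28 = 39 to Day 17 + 28 = 45. The earliest follow-up visit is Day 67, so the daily diary always covers it.

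**5. The compliance denominator.** The threshold is tied to a period of 28 days. With 28 as denominator, 0.8 × 28 = 22.4, so 23 documented days pass (82.1%) and 22 fail (78.6%). The SAP's 24-day example scores 24/28 = 85.7% and is scaled, as the SAP says. A patient with only 10 days scores 35.7% and the period is dropped.

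**6. Size under the less likely reading.** Again assume independent uniform ±3-day offsets, with baseline also counted visit to visit.
- Periods over 28 days: 21/49 = 42.9% for performance, 3/7 = 42.9% for baseline. Mean inflation factors are 1.041 and 1.031, so much of the shift cancels in the change score. With baseline 15 and true changes of −2 and −5, the observed means are 13 × 1.0408 − 15 × 1.0306 = −1.93 and 10 × 1.0408 − 15 × 1.0306 = −5.05.
- Simulation (baseline mean 14, 16 or 20 days, SD 5; changes −2 and −5; daily counts; 66 per arm; ANCOVA on baseline; two-sided level 2 × 0.02487 = 4.97%): the mean change shifts by −0.05 to +0.11 days and its SD rises by 0.31 to 0.39. The treatment difference rises too, in one run from 2.69 to 2.80 while the SD went from 6.45 to 6.77. The ratio moves from 2.69/6.45 = 0.417 to 2.80/6.77 = 0.414. Power falls by 0.8 to 1.5 points.
- A shortcut t-test calculation with 64 per arm gives a difference of 3 × 1.041 = 3.12, SD 6.04 to 6.13, and power 0.82 to 0.83 against 0.80. It scales up the difference but holds the underlying variance at 36, so it flatters power; the simulated direction is the safer one. Both effects are small.
- With no treatment effect, each reading alone rejects in 4.8 to 5.1% of trials.
- Responder status at 30%: 1.3 to 2.0% of patients lose it and 1.1 to 1.6% gain it. At 50%: 0.6 to 0.9% lose and 0.7 to 1.0% gain.

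**The case for a change.** The best opposing case is that a primary endpoint deserves one written derivation. The V3-to-V7 label accompanies the primary endpoint throughout both documents. The 28-day sentence in SAP Section 5 was written to replace the word monthly; it gives a length, not a start day. Period totals are entered at up to 11 centers, so whatever reading a site used goes straight into the data. German subjects are analyzed unblinded before final closure, with results passed to an unblinded person at the sponsor (SAP Section 4.7). Under no effect, taking the better of the two readings would raise the error rate to 5.8 to 6.2%, and their treatment estimates differ with an SD of 0.21 to 0.27 days.

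Part of this stands. The visible text does not say whether the V3 day counts, gives no start for the follow-up window, and leaves the denominator of 28 to be inferred. The rest carries less weight. Nothing in either document says that sites counted visit to visit. Investigators enter the totals under blinding. The 5.8 to 6.2% describes someone re-abstracting paper diaries after unblinding and keeping the more favorable result, which the plan does not provide for. The pCRF, the diary form, the source-data document named in Protocol Section 14.2 and SAP Appendix A are not in the text available here. A day-level convention may well sit there.

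Scaling long periods as well as short ones would not be a clean improvement. Under the same uniform assumption only 7/49 = 14% of visit-to-visit periods last exactly 28 days. If such scaling counts as imputation, about 86% of patients would fail the per-protocol criterion.

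**Conclusion.** The concern does not call for a change. Read together, the per-protocol criterion, the 28-day statement in SAP Section 5, the 28-day screening phase, and the use of 28 as both trigger and multiplier describe a fixed 28-day window from V3. The V3-to-V7 wording then serves as its nominal label, Day 14 to Day 42. On that reading no period can be too long and the effect is zero. What remains is whether the V3 day itself counts, which moves the window by one day alike in both arms, and the start of the follow-up count, which serves exploratory endpoints only. These are conventions that analysts settle when they specify the derivation.

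If sites did count visit to visit, the cost is about 0.8 to 1.5 points of power and a few responder reclassifications in each direction, with no bias between arms and type I error near its nominal level. Those figures rest on assumed headache-day rates and uniform, independent ±3-day offsets; at ±1 day the power loss is 0.1 to 0.3 points. They would not hold if visit timing differed by arm, which blinding makes unlikely.
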